[name], Internal Medicine

[name], DO, Family Medicine Resident

Protocol Date: 1/30/19

Falls Risk and Vitamin D

Background

Vitamin D is a fat soluble vitamin that is converted in the liver to 25(OH)D (circulating form) and then in the kidney to 1,25-dihydroxyvitamin D (active form). Elderly people do not convert Vitamin D effectively from the sun and instead will need to receive it from their diet or supplementations. It has been recommended to have a minimum level of 25(OH)D concentrations of 30 ng/ml to minimize risk of falls and fractures.⁶ When Vitamin D levels dip to <10 or <20 ng/ml in older adults, this is seen with muscle weakness.² This is when supplementation is necessary. Most supplements come in two forms of Vitamin D: ergocalciferol (D2) and cholecalciferol (D3). Some studies have suggested that D3 increases serum 25(OH)D more effectively than D2, so currently recommend supplementation with D3. They also do not recommend taking pure calcitriol due to hypercalcemia and/or hypercalciuria. The safe upper limit for Vitamin D is 4000 IU/day. Side effects of too much Vitamin D supplementation include: hypercalcemia, hypercalciuria, kidney stones, and it may increase risk of cancers, mortality, and falls.⁷ One out of three people aged 65 years or older fall each year, and many falls are associated with serious injury.⁵ About 20% of falls lead to injury requiring medical attention. Low serum 25(OH)D levels are associated with increased bone loss and risk of fractures as well as increased fall rates.⁹ Falls happen more consistently when 25(OH)D levels are <20 ng/ml.¹

Since it has been established that Vitamin D supplementation is important, the question then becomes how much and how often. In a study done by Zheng, et al, high dose, intermittent Vitamin D supplementation was ineffective in preventing mortality, and no benefit was seen in fracture and fall prevention. The negative effects from high doses may arise due to failure to maintain serum Vitamin D concentrations over time.¹⁰ Some meta-analyses conclude that 700-800 IU of Vitamin D daily reduces fracture risk by 13-26%, while other studies show that it's ineffective. In a study performed by Sanders, et al, participants receiving annual high-dose oral cholecalciferol experienced 15% more falls and 26% more fractures than the placebo group, and the increased likelihood of falls was exacerbated in a 3-month period immediately after annual dose. They did see an 11-19% reduction of fall risk with supplementation of Vitamin D of 700-1000 IU daily.⁸ In a study by Grgis, et al, they saw that compared with placebo, higher doses of Vitamin D (700-1000 IU) reduced falls risk by 19%, but lower doses had no effect.³ A study by Uusi-Rasi et al also showed that high 25(OH)D levels have increased risk of falls and fractures, suggesting negative influences on balance and mobility.⁹

Since there seem to be discrepancies on what levels are helpful and the frequency of supplementation, the American Geriatrics Society created some guidelines for Vitamin D usage and fall prevention. Clinicians should recommend Vitamin D supplementation of at least 1000 IU as well as Ca supplementation to community-dwelling older adults (≥ 65 years old) to reduce the risk of fractures and falls. Serum 25(OH)D concentration of 30 ng/ml should be a minimum goal for older adults, particularly for frail adults, who are at higher risk for falls, injuries, and fractures. Clinicians should not recommend large bolus

doses of Vitamin D2 or D3 $\geq 300,000$ IU. Annual doses of Vitamin D2 or D3 in autumn or winter are not recommended.⁴

Our study is aimed at conducting a retrospective chart review of patients with a diagnosis of falls. Then we will look at the characteristics of the population, specifically Vitamin D levels, supplementation, referrals to therapy and frequency of falls. Our secondary objective is to determine if supplementation with Vitamin D increases or decreases risk of falls, and at what dosage and frequency.

Objectives

The primary objective of the study is to conduct a retrospective chart review of patients with a diagnosis of falls, and to determine characteristics of the population, specifically, Vitamin D levels, supplementation, and referrals to therapy.

Also to determine if supplementation with Vitamin D increases or decreases risk of falls.

Setting of the Human Research

This study is a combination of retrospective for part 1, survey implementation for part 2, and retrospective again for part 3, and all data will be reviewed and conducted using the electronic health records of The Guthrie Clinic.

Study Design

a. Recruitment Methods:

In part 1 of the study, a retrospective chart review was performed to see how providers handled fallers. A list of patients was selected whose providers had used a variant of the ICD-10 code for fall for their GC visit of FM or IM providers, from the period of January 8, 2016 to November 29, 2017. The patients were stratified according to demographics, BMI, Vitamin D and Ca levels, polypharmacy (defined as more than 4 medications), treatment chosen (supplementation and/or referral to therapy), and cause of fall. The data was then analyzed looking for trends.

In part 2 of the study, an anonymous paper survey was administered to GC providers from IM and FM to evaluate any barriers to Vitamin D supplementation and other treatment options including therapy. Providers who complete the survey will be provided a \$10 gift card for their time involved to complete the survey. A grant application has been approved by the Donald Guthrie Foundation to cover the cost of the gift cards. The survey is administered pre and post education. The post education survey is a shorter version than the pre survey.

In part 3 of the study, new guidelines were established for GC. The IM and FM providers were educated on the new guidelines. After a period of 12 months, another review was performed of patients with ICD-10 codes related to fall to see if referrals and Vitamin D usage had changed.

b. Inclusion and Exclusion Criteria

Patients 65 years and older with a history of falls

c. Study Timelines

See above.

d. Procedures involved in the Human Research

Data will be collected from the electronic medical record. Data will include: Name, Medical Record number, Gender, Age, BMI, Encounter Date, Visit Provider, Visit Location; Diagnosis code related to falls and encounter diagnosis name.

Survey risks: anonymous, optional survey will be given to all providers.

Risks to participants

By design, there is a minimal risk to the participants in this study. However, there is always a small chance of data becoming unsecured. To minimize this possibility, all protected health information will be de-identified before results are shared. Any identifiable data will be accessed using only Guthrie computers, which are secured by the Guthrie network.

Potential benefits to participants

Analyzing data of patients with a history of falls will help increase the knowledge of how to prevent falls in high risk patients.

Provisions to maintain the confidentiality of the data

Any confidential information regarding patients will only be accessed on Guthrie computers, which are backed up through the Guthrie network. All data collection, storage, and analysis will also take place on Guthrie computers. A username and password is required to use EPIC, the software used to access patient health records. Furthermore, before any results are shared, any information that could potentially identify a patient (name, MRN, etc.) will be removed from the data.

Surveys will be completed in a de-identified manner.

Consent process/Process to document consent

A waiver of consent is being requested from the IRB for the review of medical records.

Implied consent will be obtained for the survey.

References:

1. Annweiler, C., & Beauchet, O. (2015). Questioning vitamin D status of elderly fallers and nonfallers: a meta-analysis to address a 'forgotten step'. *Journal of Internal Medicine*, 277, 16-44. doi:10.1111/joim.12250
2. Bouillon, R., MD, PhD, FRCP. (2017, October 02). Vitamin D and extraskeletal health. Retrieved November 21, 2017, from https://www.uptodate.com/contents/vitamin-d-and-extraskeletal-health?source=search_result&search=vitamin%20d&selectedTitle=5~150
3. Girgis, C. M., Clifton-Bligh, R. J., Turner, N., Lau, S. L., & Gunton, J. E. (2014). Effects of vitamin D in skeletal muscle: falls, strength, athletic performance and insulin sensitivity. *Clinical Endocrinology*, 80, 169-181. doi:10.1111/cen.12368

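### The fall-risk objective for Vitamin D cannot be answered: all sampled patients are fallers, supplementation is partly recorded as a response to the fall, and the SAP has no falls analysis

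*Protocol*

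**What the plan says.** The objective appears twice in the Protocol. The Objectives section has "Also to determine if supplementation with Vitamin D increases or decreases risk of falls". The last paragraph of the Background calls it secondary and words it more fully: "determine if supplementation with Vitamin D increases or decreases risk of falls, and at what dosage and frequency". The same paragraph lists the characteristics to be described: "specifically Vitamin D levels, supplementation, referrals to therapy and frequency of falls".

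The sample is set out under Study Design. For part 1, Recruitment Methods says "A list of patients was selected whose providers had used a variant of the ICD-10 code for fall". Part 3 again reviews patients with fall codes, to see whether referrals and Vitamin D use changed after provider education. The only eligibility line is "Patients 65 years and older with a history of falls".

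Part 1's purpose is given as "a retrospective chart review was performed to see how providers handled fallers", and its stratification variables include "treatment chosen (supplementation and/or referral to therapy), and cause of fall". That part is reported as finished: "The data was then analyzed looking for trends".

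The SAP describes provider surveys before and after education. It names chi-square or Fisher's exact tests for categorical pre/post results and a two-sample t-test for Likert means.

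**The concern.** The objective is a causal question about direction, dosage and frequency. To answer it, a study needs an outcome that can differ between patients, an exposure that precedes that outcome, and an analysis that links the two. The plan appears to have none of these.

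The risk is over-interpretation. The Background cites evidence of both benefit and harm, part 1 has already been searched for trends, and the section on potential benefits presents these fallers' data as a source of knowledge about preventing falls. With the objective left in place, the share of fallers who were supplemented, or a change in prescribing after education, could be reported as evidence for or against Vitamin D.

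**Working it through.** The documents give no sample size, effect size or event count for this objective, so there is no stated figure to reproduce. The check sets the design against the question.

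**1. Selection.** Suppose the sample has n1 supplemented and n0 unsupplemented patients. Each entered because of a fall, so:

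- risk if supplemented = n1/n1 = 100%
- risk if unsupplemented = n0/n0 = 100%
- risk ratio = 1.00 and risk difference = 0, for any true effect.

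**2. What a fallers-only sample does show.** It gives s, the share of fallers who are supplemented. Let p be the supplementation prevalence in the source population and RR the true risk ratio. The baseline risk cancels, and with confounding ignored:

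- s = p·RR / (p·RR + 1 − p)
- so RR = s(1 − p) / [p(1 − s)], and p = s / [s + RR(1 − s)].

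The plan does not collect p. The table gives the p that makes each RR fit the same s. The values of s are assumptions. The RRs come from figures cited in the Background: an 11–19% reduction gives 0.89 to 0.81, and 15% more falls is taken as about 1.15. Those figures concern different regimens and serve only as a plausible range.

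| Assumed s | p for RR 0.81 | p for RR 0.89 | p for RR 1.00 | p for RR 1.15 |
|---|---|---|---|---|
| 30% | 34.6% | 32.5% | 30.0% | 27.2% |
| 40% | 45.2% | 42.8% | 40.0% | 36.7% |
| 50% | 55.3% | 52.9% | 50.0% | 46.5% |

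For example, at s = 40% and RR = 0.81, p = 0.40 / (0.40 + 0.81 × 0.60) = 0.40 / 0.886 = 45.2%. In the other direction, at s = 40%:

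- p = 30% gives RR = (0.40 × 0.70) / (0.30 × 0.60) = 1.56
- p = 50% gives RR = (0.40 × 0.50) / (0.50 × 0.60) = 0.67.

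The same data fit benefit, no effect or harm.

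**3. Timing.** Treatment chosen in handling a fall comes after the fall that selected the patient, so it cannot have affected that fall. Supplementation is also listed as a population characteristic, but without stated timing, so earlier use is not separated from later prescribing.

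**4. Dosage and frequency.** Study Design, section d, lists 10 items: two identifiers, three patient descriptors (gender, age, BMI), three visit details (date, provider, location) and two diagnosis fields. None records supplement use, dose, frequency or start date, and none is defined as a later fall. Part 1's stratification shows that supplementation and Vitamin D level were recorded in some form, but it names no dose, start date or use before the fall. Dosage as something to be measured appears only in the SAP's second provider survey. If that is the Protocol's part 2 survey repeated after education, it is anonymous and cannot be linked to any patient's falls.

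**5. Analysis.** Of the SAP's two kinds of test, none has falls as an outcome. None compares supplemented with unsupplemented patients, and no confounder adjustment is described.

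**The case against.** The strongest reply is that fallers-only sampling does not rule out every analysis of supplementation and falls. Fall frequency is listed as a characteristic, and record number, visit date and fall code are collected, so repeat fall-coded visits could be counted and would vary between patients. On this view the risk ratio of 1.00 is a tautology, and the real gap is missing specification. It is true that the figure applies only to the qualifying fall and that a recurrence analysis is conceivable. But recurrence among fallers is a narrower question than the risk of falling. It would also need a time zero, a follow-up window, dated exposure and adjustment for why providers chose to supplement, and none of these is planned.

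Three further points limit the supporting evidence:

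- The 10-item list is plainly incomplete, since it also omits Vitamin D level and referral, which part 1 used. The zero count is accurate but secondary.
- The Protocol does not say whether the part 3 review captures dose, and the link between the SAP's second survey and the anonymous survey is inferred.
- The benefit statement is generic and does not mention Vitamin D.

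It can also be said that this is a secondary objective in a minimal-risk study, and that no planned test would produce a misleading falls estimate. That limits the damage to this objective. It does not supply a way to meet it.

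**Conclusion.** The concern holds. As written, and under the plan as documented, the objective cannot be answered in direction, dosage or frequency. The main reasons are structural and need no assumed values: the risk of the qualifying fall is 100% in both groups, treatment chosen after the fall cannot have affected it, and 0 of the SAP's 2 kinds of test address falls. The table in the working is illustrative and rests on assumed shares of supplemented fallers.

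The fault is confined to this objective. The description of Vitamin D levels, supplementation and referrals stands, as does the comparison of practice before and after education.

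**What to change.** Issue a dated amendment that gives the reason and notes that part 1 had already been analysed. In both the Background and the Objectives section, do one of the following:

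1. Delete the fall-risk objective, including its dosage and frequency clause.
2. Replace it with a descriptive one, for example: *To describe Vitamin D levels, supplementation and therapy referrals among patients aged 65 or older with a fall-coded visit, and the change in referrals and Vitamin D usage after provider education.*

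In either case add: *This study does not estimate the effect of Vitamin D on the risk of falls, and no conclusion on that effect will be drawn.* Bring the statement of potential benefits into line with that limit; this edit is the less important one.

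The cost is wording only: no new data, no change to parts 1 to 3 and no planned analysis lost. The study gives up a secondary claim that it could not have supported.

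If the sponsor wants evidence on falls, a recurrence analysis among fallers should be a separate exploratory proposal. It would need its own cohort, time zero, exposure and outcome definitions, adjustment (including therapy referral and prior falls) and further chart abstraction.

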### **Statistical Analysis Plan January 30, 2019**

Survey providers from Internal Medicine (IM) and Family Medicine (FM) to evaluate fall treatment. Educate providers on new protocol. Survey results will be analyzed and used to develop to develop educational care protocol for treatment which will be communicated to providers at grand rounds.

Twelve months after grand rounds, a second survey of IM and FM providers will be conducted to determine how well physical therapy referrals and Vitamin D supplementation dosages aligned with the established protocol.

Associations between pre/post results for categorical variables will be tested with chi-square or Fisher's Exact test.

For comparisons of means for Likert variables, a two sample t-test will be used.

Statistical analysis will be completed using R statistical software program. R Core Team (2019). R: A language and environment for statistical computing. R Foundation for Statistical Computing, Vienna, Austria. URL <https://www.R-project.org/>.

Statistical significance is defined as a p value of 0.05 or less.

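### Both chart samples are defined by fall codes, entered in Part 1 by the provider groups who are then educated, so a coding shift could create, mask or shrink the pre/post change

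*Protocol*

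**What the plan says.** In the Protocol, Study Design, a. Recruitment Methods, Part 1 lists patients "whose providers had used a variant of the ICD-10 code for fall". The visit must be with an FM or IM provider, and the dates run from 8 January 2016 to 29 November 2017. In Part 3 the intervention is delivered: "The IM and FM providers were educated on the new guidelines". The follow-up, a year later, is then described: "another review was performed of patients with ICD-10 codes related to fall to see if referrals and Vitamin D usage had changed".

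Eligibility (section b) is a history of falls at age 65 or over. No way of finding fallers other than the code is described. The data list in section d includes the fall code and encounter diagnosis, but names no independent record of a fall.

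The only test in the SAP that could apply to referral or supplementation is this: "Associations between pre/post results for categorical variables will be tested with chi-square or Fisher's Exact test". The SAP mentions no code list, check on coding frequency, case-mix adjustment or comparison group. It also does not mention the chart review: it assigns the 12-month question about referrals and Vitamin D dosages to a second provider survey.

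**The concern.** The people who receive the intervention also enter the code that admits a patient to the Part 1 sample, and Part 3 samples by code again. Teaching providers about fall care could affect two things: what they do for a faller, and whether they record a fall code at all. A pre/post comparison of proportions among coded patients cannot separate the two.

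The shift could go either way. If more minor falls are coded after education, the referral proportion falls with no change in care, or a real gain is hidden. If a fall is coded mainly when the provider acts on the guideline, the proportion rises with no change in care. The protocol's conclusion on whether practice changed after education is what is at stake.

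The sampling rules also differ on paper. Part 1 is restricted to FM or IM visits and has dates; Part 3 repeats neither.

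**Working it through.** The documents give no referral rate, coding rate, sample size or effect size, so there is no figure to reproduce. Every rate and sample size below is an assumption, used only to see how large a pure coding effect could be.

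**1. More minor falls coded, care unchanged.** Assume 30% of coded patients are referred before education. Afterwards, extra patients with minor falls are coded, equal to a fraction x of the original sample, and 10% of them are referred. The measured proportion is (0.30 + 0.10x)/(1 + x).

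| x | Measured proportion | Spurious change |
|---|---|---|
| 0 | 30.0% | 0 |
| 0.2 | 0.32/1.2 = 26.7% | −3.3 points |
| 0.3 | 0.33/1.3 = 25.4% | −4.6 points |
| 0.5 | 0.35/1.5 = 23.3% | −6.7 points |

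**2. A second model with explicit coding probabilities.** Assume 30% of fallers are complex (50% referred) and 70% simple (20% referred). The proportion referred among coded patients is the sum of share × coding probability × referral rate, divided by the sum of share × coding probability. With coding probabilities of 0.60 (complex) and 0.20 (simple) before education, it is (0.18×0.50 + 0.14×0.20)/(0.18 + 0.14) = 0.118/0.32 = 36.9%.

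- Care unchanged, simple-fall coding rises to 0.30, 0.40 or 0.60: 33.8%, 31.7% or 29.0%, a change of −3.0, −5.1 or −7.9 points. With 400 charts per period, the last would test significant at two-sided 0.05 about 66% of the time (39% with 200, 22% with 100).
- Care unchanged, complex-fall coding rises to 0.75 or 0.90: 38.5% or 39.8%, a change of +1.6 or +2.9 points.
- True gain of 8 points in both types, simple-fall coding rises to 0.30, 0.40 or 0.60: the observed gain shrinks to 5.0, 2.9 or 0.1 points.

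**3. Coding that follows the decision to treat.** Of 100 coded fallers, suppose 30 are referred and 70 are not. If 20% fewer of the unreferred are coded and care is unchanged, the proportion becomes 30/(30 + 56) = 34.9%, a spurious gain of 4.9 points.

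**4. What adjustment can do.** In step 2 the rates within each type stay at 50% and 20% when care is unchanged, so adjusting for type would remove the bias if type were measured. In step 3 selection is on the outcome itself, and no baseline covariate removes it.

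**The case against.** The strongest reply is that the mechanism is possible but not documented. Nothing says the education covered coding; the protocol speaks of guidelines and the SAP of a treatment protocol. No coding rate is given for either period, and if coding is unchanged the bias is zero. This stands, and limits the point to what could happen.

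Second, the SAP's chi-square sentence may refer to survey answers, where no patient is selected by code. This also stands. A reader might infer that the plan commits to a crude test of chart proportions, but the chart comparison has no clearly assigned test. The protocol still states the comparison, so the exposure remains and the two documents need reconciling.

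Third, a reader might infer that the conclusion would be wrong in sign. The documents do not support that. Step 1 has no true change to reverse. Adding an equal true gain g to both groups makes the observed change g minus 3.3, 4.6 or 6.7 points, so reversal requires a true gain below those assumed figures. The 8-point gain in step 2 shrinks but never reverses.

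Fourth, a reader might infer two different code lists from the differing phrases, "whose providers had used a variant of the ICD-10 code for fall" in Part 1 and "another review was performed of patients with ICD-10 codes related to fall" in Part 3. These may be loose paraphrases of one list. The firmer differences are the missing visit restriction and dates.

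Finally, the available covariates do not include fall severity, so adjustment is only a partial remedy. That stands and should be stated in the SAP.

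**Conclusion.** The point holds as a design weakness with no safeguard in either document. A coding change after education could create, mask or shrink a pre/post difference in referrals or Vitamin D use, and the plan has no means of detecting it. Under step 1 the spurious drop is about 3 to 7 points. The second model gives −7.9 to +2.9 points with care unchanged. These ranges rest wholly on assumed rates; the actual size and direction are unknown. The documents do not establish that coding changed or that the result has the wrong sign.

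Separately, two matters need reconciling on the face of the documents: Part 3's sampling rule against Part 1's, and the protocol's chart review against the SAP's survey as the source for the 12-month question.

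**What to change.** - Reconcile the protocol and SAP on whether the 12-month question is answered from charts, the survey or both, and assign an analysis to each.
- Apply one ICD-10 fall code list, the same FM/IM visit restriction and a stated date window to both periods. Visit provider and location are already on the section d data list.
- Report fall-coded patients aged 65 and over per 1,000 IM/FM visits by patients of that age, by period. A rate is needed because the Part 1 window is nearly 23 months and the Part 3 window is not given.
- Tabulate case mix by period, since it can change while the coding rate stays constant.
- Analyse referral and supplementation with a logistic model for period, adjusted for age, gender, BMI, polypharmacy and cause of fall, alongside the crude test. Part 1 already used the last two, but section d does not list them; extract them in Part 3 as well.
- State that adjustment cannot remove selection on unmeasured severity or on the decision to treat, so a shift in coding rate or case mix limits the conclusion.

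The cost is one count query, two variables added to the data list, and a model to fit and explain where a simple chi-square might have served. Referrals and Vitamin D orders per 1,000 visits of all patients aged 65 and over would not depend on fall coding, but would extend the data scope beyond fallers, so they are optional.

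### The Part 3 chart review asks whether Vitamin D usage changed; the SAP's 12-month aim is alignment with the taught protocol, assigned to a survey, so no chart outcome measures agreement with the guideline

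*Protocol*

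**What the plan says.** **Protocol, Study Design, a. Recruitment Methods.** In Part 3, new guidelines are set for the clinic, internal medicine and family medicine providers are taught them, and 12 months later the charts of patients with fall codes are looked at again "to see if referrals and Vitamin D usage had changed". Usage is not defined. For the baseline review (Part 1), the treatment variable records only whether the provider chose supplementation, referral to therapy, or both.

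**SAP, first and second paragraphs.** The SAP has the care protocol taught at grand rounds. Its 12-month step is a repeat survey of the same two provider groups. The stated purpose of that survey is to "determine how well physical therapy referrals and Vitamin D supplementation dosages aligned with the established protocol". It does not define alignment and does not mention a chart review. Categorical pre/post results are to be compared by chi-square or Fisher's exact test, with significance at p of 0.05 or less.

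**Protocol, Background.** Regimens are not treated as interchangeable. One cited study is summarised as finding that "higher doses of Vitamin D (700-1000 IU) reduced falls risk by 19%, but lower doses had no effect". From the cited society guideline the protocol reports that "Annual doses of Vitamin D2 or D3 in autumn or winter are not recommended". Of excess supplementation it says that "it may increase risk of cancers, mortality, and falls".

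The content of the guideline that was actually taught appears in neither document.

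**The concern.** The education teaches a particular way of treating patients who fall, so the natural outcome is whether patients are then treated that way. The SAP recognises this, but asks the question of providers. The protocol looks at patients' records, but asks only whether usage moved. What providers report and what the chart shows need not agree, and the chart is the more direct evidence of practice.

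A change in usage also has no clear favourable direction. On the protocol's own reading of the literature, some regimens do nothing and some may do harm, so more use is not necessarily better use. Part 3 could report no effect when practice had moved towards the guideline, or report uptake when the added use lay outside it.

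**Working it through.** **1. The two 12-month evaluations side by side.**

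| | Protocol, Part 3 | SAP |
|---|---|---|
| Source | Charts of patients with fall codes | Second provider survey |
| Question | Did referrals and usage change? | Did referrals and dosages align with the protocol taught? |
| Direction or standard | None stated | The established protocol |
| Key term defined? | No (usage) | No (alignment) |

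The charts have no agreement criterion, and the agreement criterion has no charts.

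**2. What follows if usage is coded yes/no.** Let U be the proportion of fall-coded patients on any Vitamin D, C the proportion on a concordant regimen and N the proportion on a non-concordant one. Then U = C + N, so change in U = change in C + change in N. A null change in U is compatible with any offsetting changes in C and N. If U is the same in both periods, the change in C can lie anywhere from −U to +U.

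**3. Illustration.** The documents give no sample size, usage rate or regimen mix, so there is no planned figure to reproduce. Every input below is an assumption: n = 100 charts per period, different patients in the two periods, two-sided 0.05, Pearson chi-square without continuity correction. With equal n, chi-square = n(p2 − p1)² / [2 p̄(1 − p̄)], where p̄ is the mean of p1 and p2.

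*Case A, regimens corrected among existing users.*
- Any use 40% to 40%: chi-square = 0, p = 1.0.
- Concordant use 10% to 30%: p̄ = 0.20, chi-square = 100 × 0.04 / (2 × 0.16) = 12.5, p = 0.0004.

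*Case B, non-concordant use added.*
- Any use 40% to 60%: p̄ = 0.50, chi-square = 100 × 0.04 / (2 × 0.25) = 8.0, p = 0.005.
- Concordant use 10% to 10%: chi-square = 0, p = 1.0.

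With continuity correction the two non-zero statistics become 11.28 (p = 0.0008) and 7.22 (p = 0.007), so the reading is the same.

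**4. Range.** With use fixed at 40%, the change in concordant use is 0.40 times the change in the share of users who are concordant. A shift in that share of 0, 0.25 or 0.50 gives 0, 10 or 20 points; Case A is the last (0.25 to 0.75). Power over assumed numbers of charts:

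| Charts per period | Concordant use 10% to 30% (Case A) | Any use 40% to 60% (Case B) |
|---|---|---|
| 50 | 0.71 | 0.52 |
| 100 | 0.95 | 0.81 |
| 200 | 0.999 | 0.98 |

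More charts do not help: in Case A the usage comparison has no difference to detect, and in Case B they make the misleading result more likely.

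**5. If usage is coded by dose and frequency,** neither misreading is forced. The result then depends on how regimens are grouped, which is also unspecified.

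**The case against.** The strongest reply is that the plan contains no yes/no rule. The Background uses the same word, usage, to introduce society guidelines that go on to dose and dosing interval, and its closing paragraph gives a secondary objective that covers dosage and frequency (tied to fall risk, not to agreement with a guideline). This stands: the misreadings are possible, not certain. A yes/no coding remains plausible because the Part 1 variable is that coarse, and nothing written rules it out.

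A reader might infer three stronger things that the documents do not support.

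- *That dose will not be collected, because section d (Procedures involved in the Human Research) lists no dose or frequency.* That list also omits Vitamin D level and referral, although Part 1 stratified patients by Vitamin D level and by treatment chosen, including referral. It is plainly not exhaustive.
- *That the Background gives conflicting triggers for supplementation, so a rise in use cannot be interpreted.* The 30 ng/ml figure is a minimum or goal, not a trigger, and none of these statements is said to be the guideline taught. The benchmark is the adopted guideline.
- *That the plan ignores agreement with the guideline.* The SAP names it; the difficulty is where it is measured.

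It is also fair to say that the stated primary objective is descriptive, that Part 3 is not designated a primary endpoint, and that Cases A and B are deliberately clean examples. Nothing shows that non-concordant regimens are common in this clinic.

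**Conclusion.** The concern holds in a limited form. The protocol and SAP give different questions and different data sources for the 12-month evaluation, and neither defines its key term. As written, no chart outcome measures the SAP's stated aim, so Part 3 cannot be relied on to show whether the guideline was taken up.

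The two specific misreadings rest on a yes/no coding of usage. Their size is unknown: the 20-point contrasts show what could happen under assumed rates and do not estimate what will happen. It is also an assumption that the adopted guideline disfavours the regimens that the Background reports as advised against. The change is worth making because it is cheap relative to the ambiguity it removes.

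**What to change.** 1. Reconcile Part 3 of the protocol with the second paragraph of the SAP. State which 12-month question the survey answers and which the chart review answers, and bring the chart review into the SAP.
2. Keep simple usage and referral as descriptive measures, and define usage. Beside them, add the proportion of fall-coded patients whose recorded Vitamin D regimen (product, dose and frequency) and referral match the adopted clinic guideline.
3. Take the definition of concordance, including how patients without supplementation are scored, from the written guideline, not from the Background or from this review.
4. Score Part 1 and Part 3 charts by the same rule and compare the proportions by the planned chi-square or Fisher's exact test.
5. Report non-concordant use separately, with a category for regimens that cannot be classified.
6. Name product, dose, frequency and referral in the section d data list.

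**Cost.** Wording changes in both documents and some further abstraction. The Part 1 review is described as already performed and analysed, so those charts may have to be reopened for regimen details. Over-the-counter doses may be missing from some records, which is why the unclassifiable category is needed.
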